▲ If an in-hospital patient recovering from another primary procedure NOT previously included undergoes emergency surgery, this **MUST** be included in the study as emergency case. ▲

i.e. Patient A is recovering from an AAA repair and undergoes large bowel resection due to bowel ischaemia one day later the previous surgery. He was correctly not included after the AAA repair, as that is a primarily vascular procedure and it did not involve any large bowel resection, but should be included after the bowel resection.

- ▲ You should collect data on consecutive elective patients operated at your hospital during the data collection period. **All eligible patients** must be included. Strategies to identify consecutive patients could include: ▲
- Daily review of elective theatre lists.
 - Daily review of handover sheets and ward lists.
 - Daily review of theatre logbooks
 - Daily on call review of patients undergoing emergency surgery

7. Outcome Measures

I. Primary outcome measure:

- Adherence to selected Enhanced Recovery After Surgery (ERAS) guidelines regarding rate of routine prophylactic drain insertion in colorectal surgery (22).

II. Secondary outcome measures:

- Rate of intra-abdominal postoperative collections, defined as collections which alter the normal postoperative course (e.g. requiring either medical, radiological, endoscopic or surgical intervention) (23).
- Time-to-diagnosis (days) of intra-abdominal postoperative collections defined as collections which alter the normal postoperative course (e.g. requiring either medical, radiological, endoscopic or surgical intervention) (23).
- Rate of drain-related complications defined as:
 - Surgical site infection (Centers for Disease Control and Prevention – CDC – definition: A surgical site infection is an infection that occurs after surgery in the part of the body where the surgery took place);
 - Cutaneous irritation at the drain insertion site (defined as reversible damage of the skin associated with rash, dry skin, itchiness, red discolouration and/or hives);
 - Small bowel evisceration and herniation of omentum (defined as prolapse of small bowel and/or omentum through the drain site after the removal of the drain);
 - Bowel injury (defined as intraoperative identification of or CT-proven drain-related iatrogenic bowel perforation) (7,24).

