Intraoperative complications	None / Vascular injury / Bowel injury (e.g. duodenum) / Injury to other organs or structures (e.g. ureter)
Abdominal drain(s) inserted at time of surgery	Yes / No
Reason for drain identified	
Not identified Excessive intraoperative blood loss (or concern regarding this). Excessive intraoperative fluid (not blood) collections (or concern regarding this). Contaminated or dirty surgery

	
Positive air leak test (the intra-operative air leak test is a common intraoperative test used to identify mechanically insufficient anastomosis)
 
Poor vascularisation of the anastomosis (determined visually or by ICG fluorescence) (or concern regarding this).
 
Other reason identified (please specify)

Number of drains	Number
Type of drain(s) used	
Open (open drains drain fluid on to a gauze pad or into a stoma bag e.g. Penrose) / Close (tubes draining into a bag or bottle, e.g. Jackson-pratt).
 
Active (drains maintained under suction) / Passive (drains that have no suction and work according to the differential pressure between body cavities and the exterior).
 
(see REDCap for pictures)

Drain location	
Subcutaneous drain
 
Intraabdominal drain – pelvis
 
Intraabdominal drain – peritoneal cavity
 
Intraabdominal drain – posterior to the anastomosis
 
Intraabdominal drain – anterior to the anastomosis
 
Intraabdominal drain – near the anastomosis (not in contact)

Daily postoperative data points (to be completed for each inserted drain)	Required data (definition / comment)
Day of surgery is defined as Post-operative Day (POD) 0. The day after surgery is therefore defined as POD 1 and day 10 after surgery as POD 10.	
Volume drained (Daily POD 1-10)	
Millilitres (recordings of drain output must correspond to the entire day, i.e. 8am to 8am).
 
It is recommended that you collect data one day in retrospect.

Contents of drain output (Daily POD 1-10)	
Serous fluid (with or without blood staining) / Frank blood / Purulent / Faecal
 
(see REDCap for pictures)

Drain-related data points	Required data (definition / comment)

Day of drain removal	Post-operative Day (POD)
Surgical site infection	Yes – Site of Drain(s) / Yes – Other incision / No As defined by US Centers for Disease Control and Prevention (CDC)

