Surgical site infection type	Yes - Superficial (skin or subcutaneous tissue) / Yes - Deep (fascial and muscle layers) / Yes - Organ/Space SSI (intrabdominal) / No .
Small bowel evisceration/herniation of omentum	Yes – Site of Drain(s) / Yes – Other incision / No Prolapse of small bowel and/or omentum through an incision.
Drain-related iatrogenic bowel perforation	Yes - Intraoperative / Yes – Postoperative (not during removal) / Yes – Postoperative (during removal) / No.
Drain-related skin irritation	Yes (reversible damage of the skin at the drain insertion site associated with rash, dry skin, itchiness, red discolouration and/or hives) / No
Other Drain-related complication	Please specify
Reason(s) for drain removal	
1. Clinical rationale:
 
a). Drain output satisfactory (Yes, No) - if yes: low volume, (haemo)serous fluid, other (please specify).
 
b). Drain-related complications.
 
c). Inadvertent/premature drain withdrawal.
 
d). Other (please specify)
 
2. Radiological confirmation of no significant ongoing collection (Yes - pre removal, Yes - post removal, No).

Post-operative blood transfusion	Yes / No
Day of blood transfusion	Post-operative Day (POD)
History of collection(s) requiring treatment within 30 days (either medical, surgical, endoscopic, radiological)	Yes / No
Day of collection(s) identification	Post-operative Day (POD)

Collection(s) identification method	
1. Clinical only
 
a). Symptoms. b). Change in drain output (if inserted at time of surgery).
 
2. Radiological
 
a). Imaging due to clinical suspicion b). Routine imaging as per hospital policy c). Incidental finding (imaging for other indication).

Collection(s) treatment	
Conservative management (none or antibiotic therapy) Percutaneous drainage Surgery

Total postoperative antibiotic duration	
Number of days (Total antibiotic duration including both intravenous and oral antimicrobial therapy for the treatment of the collection(s). Post-operative antimicrobial therapy started before the identification of the collection(s) should not be included.)

Outcome data points	Required data (definition / comment)
Anastomotic leak within 30 days	Yes - Radiological diagnosis / Yes - Surgical diagnosis / No
Day of anastomotic leak diagnosis	Post-operative Day (POD)
Length of hospital stay (days)	Days
30 day readmission	Yes / No

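### The drain-related complication rate counts any surgical site infection, with no limit to the drain site and no denominator of drained patients

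*Protocol*

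**What the plan says.** Section 7 of the protocol (Outcome Measures, secondary) introduces the outcome with the words "Rate of drain-related complications defined as" and gives four components:

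- SSI, with a general definition attributed to the CDC: "A surgical site infection is an infection that occurs after surgery in the part of the body where the surgery took place".
- Skin irritation, limited by location: "Cutaneous irritation at the drain insertion site".
- Evisceration or herniation, limited by location: "defined as prolapse of small bowel and/or omentum through the drain site after the removal of the drain".
- Bowel injury, identified during surgery or as "CT-proven drain-related iatrogenic bowel perforation".

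The outcome has no stated denominator. Section 7 also lists a separate secondary outcome: "Rate of intra-abdominal postoperative collections, defined as collections which alter the normal postoperative course".

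Appendix A records where an SSI occurred, with the answers "Yes – Site of Drain(s) / Yes – Other incision / No". A second field records its type: superficial, deep, organ/space or none. The evisceration field has the same three site answers as the SSI site field.

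**The concern.** Three of the four components can occur only because a drain was placed. The SSI component can occur in any patient who has had colorectal surgery, at the main wound or inside the abdomen. Counted as written, it puts events with no stated link to a drain into a rate labelled drain-related.

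The study audits compliance with a guideline against routine drains, so its drain-complication rate is a natural figure to cite as evidence of harm. If most of the numerator is infection away from the drain, the figure does not describe what its label says. With no stated denominator, a patient without a drain could also enter the numerator.

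**Working it through.** **The plan's own figure.** There is none to reproduce. The protocol gives no expected SSI rate and no expected drain-complication rate. The anticipated sample of about 5000 does not bear on the definition.

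**Section 7 set against Appendix A.**

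| Component | Limit in Section 7 | Field in Appendix A |
|---|---|---|
| SSI | None beyond the operated part of the body | Site: drain, other incision, no. Type: superficial, deep, organ/space, no |
| Skin irritation | Drain insertion site | Yes or no, at the drain insertion site |
| Evisceration or herniation | Drain site, after removal | Site: drain, other incision, no |
| Bowel injury | Drain-related perforation | Drain-related perforation, by timing |

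SSI and evisceration have the same site answers. For evisceration, Section 7 takes only the drain-site answer. For SSI it sets no such limit, and no reason is given for the difference.

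The block heading in Appendix A, drain-related data points, does not supply the limit. The same block holds postoperative transfusion and every treated collection within 30 days, neither of which is confined to the drain.

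The site field has no separate answer for organ/space infection, so a drain-site restriction also has to use the type field.

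**Illustration of size.** Every input here is assumed; none comes from the documents. The components are treated as non-overlapping and both rates use the same denominator. Let S be the any-site SSI rate, d the drain-site SSI rate and o the rate of the other three components.

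- Rate as written = S + o
- Rate tied to the drain = d + o
- Ratio = (S + o) / (d + o)

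*Set A:* S = 10-15%, d = 1-3%, o = 1-2%.

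- As written: 10 + 1 = 11% to 15 + 2 = 17%.
- Tied to the drain: 1 + 1 = 2% to 3 + 2 = 5%.
- Smallest ratio (S = 10, d = 3, o = 2): 12 / 5 = 2.4.
- Largest ratio (S = 15, d = 1, o = 1): 16 / 2 = 8.

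*Set B:* S = 5-15%, 10-50% of SSIs at the drain site, o = 1-3%. Here d = S × share.

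- As written: 5 + 1 = 6% to 15 + 3 = 18%.
- Tied to the drain: 5 × 0.10 + 1 = 1.5% to 15 × 0.50 + 3 = 10.5%.
- Smallest ratio (S = 5, share 50%, o = 3): 8 / 5.5 = 1.45, about 1.5.
- Largest ratio (S = 15, share 10%, o = 1): 16 / 2.5 = 6.4.
- Share of counted events that are SSIs away from the drain, (S - d) / (S + o): from (5 - 2.5) / 8 = 31% to (15 - 1.5) / 16 = 84%.

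**The case against.** The best defence is that the intended scope can be inferred. The bullet sits under a drain-related heading, its sentence explains what an SSI is rather than which ones count, and Appendix A collects the site. An analysis plan, not shown, could restrict the numerator. This stands in part: the fault lies in the outcome definition, not in data capture, and incisional SSI can be restricted with data already collected. But Section 7 does not leave the matter open. It states a definition, and nothing else in the protocol says that only the drain-site answer counts.

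A second defence is that the breadth is deliberate. The Study Background suggests that drains may promote wound infection through serous fluid and act as a route for contamination. That is a fair reason to study SSI at all sites. It is a hypothesis, though, to be examined by comparing all-site SSI in drained and undrained patients. Labelling every SSI drain-related assumes the answer.

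A third defence is that the components may be reported one by one, which Section 7 does not exclude. That would make the problem visible, but the SSI component would still carry the drain-related label.

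The documents do not support some stronger readings:

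- **That organ/space SSI and the collection outcome are one event counted twice.** A collection is defined by an altered course and treatment, not by infection, so a treated haematoma could qualify without being an SSI. An organ/space infection need not be a collection. The two overlap, but they are separate outcomes and are never summed.
- **That the form cannot record infection at two sites.** The data dictionary does not say whether the field takes one answer or several, and the REDCap form is not shown.
- **That the protocol says the drain caused these infections.** Its wording is drain-related.

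**Conclusion.** The point holds as a fault in a stated outcome definition. Followed literally, Section 7 counts SSIs at the main incision and in the organ/space as drain-related, and does not confine the count to patients with a drain.

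The direction is clear: on a common denominator, the rate as written cannot be lower than the drain-site rate, and it is higher whenever a patient with none of the drain-tied events has an SSI elsewhere. The size is not known. The figures of about 2.4 to 8 times (Set A) and 1.5 to 6.4 times (Set B) follow from assumed inputs and only illustrate the possible scale. A reader might infer that wound infection is bound to dominate the rate. With no SSI rates in the documents, that is possible but not shown.

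This affects one component of one secondary outcome. The primary outcome, adherence on drain insertion, is untouched. The definition should still be corrected, because the rate could mislead on harm from drains and the repair is simple.

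**What to change.** In Section 7:

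1. Restrict the SSI component to incisional SSI (superficial or deep in the Appendix A type field) with the drain-site answer in the Appendix A site field.
2. State that the denominator is patients who had a drain.
3. Report all-site SSI as a separate outcome in drained and undrained patients. This keeps the question raised in the Study Background.
4. Keep organ/space SSI out of the drain-related rate. Report it with all-site SSI, and note that it overlaps with the collection outcome but is not identical to it.

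The cost is a small change of outcome wording and a lower reported drain-complication rate. The existing site and type fields suffice, so no new data item is needed.

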- Time (measured in whole days) until drain removal and drain output (quantity and contents) on day of removal. Daily output will be calculated adding up the volumes drained in the 24 hours prior to the morning ward round. Contents are defined as serous fluids (with or without blood staining), frank blood, purulent and faecal.
- Overall 30-day adverse event rate as defined by the Clavien-Dindo scale of postoperative complications (25) and length of stay (days).

- ▲ Day of surgery is defined as Post-operative Day (POD) 0. The day after surgery is therefore defined as POD 1 and day 10 after surgery as POD 10. ▲

8. Measuring drain output

Drain output (volume and contents) should be assessed daily until removal or for the first ten days after surgery (Day 0: day of surgery – Day 10).

Strategies to record drain output and day of drain removal

- Speaking to ward staff, including doctors and nurses
- Reviewing patient notes daily, particularly drain charts
- Participating in daily ward rounds and doctor reviews

Remember: recordings of drain output must correspond to the entire day (8am to 8am). It is advised that you collect data one day in retrospect to capture all relevant data.

9. Covariates

Data will be collected on audit standards, and confounding factors for risk of intra-abdominal postoperative complications to permit accurate risk adjustment of outcomes. Without appropriately adjusting for risk factors, it is likely that any findings would be biased and unable to be appropriately analysed on a national scale. Data will **not** be analysed at a surgeon-level or centre-level. A full list of required data fields is available in Appendix A, and on the REDCap database.

10. Follow-up

Patients will be followed for 30 days after surgery. All secondary outcome measures will be recorded if they occurred at any point from postoperative Day 0 (day of surgery) to Day 30.

No change to routine follow up should take place. Collaborators should be proactive in identifying follow up data, but this should be done within the limits of routine follow up.

Strategies for follow-up include:

- Regularly reviewing patient notes to identify in-hospital complications.
- Participating in daily ward rounds and doctor reviews.
- Reviewing clinic notes and clinic letters, if seen in clinic by 30 days.
- Checking electronic systems and handover lists for re-admissions.
- Checking for emergency department re-attendances.

11. Data Analysis & Sample Size

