Project team structure: Medical students will take the lead in disseminating and delivering this study alongside junior doctors. These ‘mini-teams’ should be supervised by a consultant surgeon at each site (Figure 1). Each team should include at least one qualified doctor to provide additional local support for participating medical students.

Training: The protocol was formally launched at the European Society of Coloproctology (ESCP) meeting on 26th September 2019. Investigators will be trained in the study background, design, and methodology. COMPASS regional and local leads are encouraged to hold local meetings with collaborating teams at their medical school to brief them on the protocol, and to feedback any local issues or questions raised. To ensure collaborators understand the study topic, drain follow-up, inclusion criteria, application of the Clavien-Dindo classification and the principles of data governance, they will all be asked to complete a series of online e-learning modules (pass mark is 100%) prior to starting data collection.

Data completeness: Following data collection, only data sets with >95% data completeness will be accepted for pooled analysis. To emphasise the importance of data completeness to collaborators, centres with >5% missing data points will be excluded from the study and collaborators from those centres withdrawn from the published list of citable collaborators.

Validation: Data validation will be performed at a minimum of five centres in each participating country. Data validators may be either a final year student or a qualified doctor who were not involved in the initial data collection.

The validator will be assigned a random 2-week data collection period at a local centre to validate. Data validation will occur following completion of data collection (including follow-up). After completing validation, the validator will send a summary of how many records were reviewed and error rates to the study management group. There are two components of validation:

I. Case ascertainment:

- The validator will independently identify all patients eligible for inclusion over the one 2-week study period. The target for data ascertainment is >95%.

II. Data collection

- The validator will independently collect data for the key data fields relating to risk-adjustment and outcome measures (see **Appendix A**).

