Highest 30-day complication grade	
None / Clavien-Dindo Grade I-V (see Appendix C for the full Clavien-Dindo scale).
 
For Grade V please collect: Death during primary admission? Yes/No Postoperative day of death: _____ day

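### The removal-day field has no entry for a drain still in place at death, discharge, transfer or POD 30, so the longest drain durations tend to drop out of time to drain removal

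*Protocol*

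**What the plan says.** Protocol section 7 defines the outcome as "Time (measured in whole days) until drain removal and drain output (quantity and contents) on day of removal". It serves the secondary aim, in section 3, on when drains can safely come out.

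Appendix A holds the data for it under the drain-related data points. The field "Day of drain removal" has one permitted response, a postoperative day. A separate item gives the reason for removal, and its options include "Inadvertent/premature drain withdrawal" and "Drain-related complications". For Clavien-Dindo grade V the form also asks for "Postoperative day of death".

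Section 10 sets the window: "Patients will be followed for 30 days after surgery", and "All secondary outcome measures will be recorded if they occurred at any point from postoperative Day 0 (day of surgery) to Day 30". Follow-up stays within what is routine at the centre.

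On completeness, section 14 says that "centres with >5% missing data points will be excluded from the study". Appendix D, step 9, tells collectors to fill in all fields. It states the 5% limit as a share of patients, not of data points, with loss of authorship if it is exceeded.

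**The concern.** A time-to-event outcome needs two pieces of information per patient: whether the event was seen, and the day of the event or the last day on which it was known not to have happened. Appendix A collects only the day. For a patient who goes home with a drain, is transferred with it, dies with it in place or still has it at POD 30, no valid response is offered.

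The collector can leave the field blank, which the completeness rules discourage, or enter a day on which no removal took place. A blank removes the patient from the outcome. An invented day, such as the day of discharge, shortens the duration. Both act mainly on drains that stay in longest, so the distribution is trimmed at its upper end. That end matters for a description of drain practice and for the aim on safe removal.

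A later analysis plan cannot repair this. Whatever rule it adopts for drains not seen to be removed, it needs drain status as an input, and that status may not be recoverable once collection has closed.

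**Working it through.** **1. How Appendix A handles the other event days**

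| Event | Item saying whether it happened | Day field |
|---|---|---|
| Postoperative blood transfusion | Yes / No | POD |
| Collection needing treatment | Yes / No | POD |
| Anastomotic leak | Yes (two forms) / No | POD |
| Death | Clavien-Dindo grade V | POD |
| Drain removal | none | POD |

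For the first four, an empty day field can be read from the item before it. For drain removal it cannot. In a patient who died, a blank removal day can be interpreted from the recorded day of death. In a survivor it could mean discharged or transferred with the drain, still drained at POD 30, or simply not recorded. No field separates these.

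**2. What a blank could cost a centre**

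Section 11 expects three patients per centre per week, so 3 x 2 = 6 per 14-day period.

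- Limit read per patient (Appendix D, step 9): one patient with a blank is 1/6 = 17%, above 5%. A centre running all four main periods has about 24 patients: one such patient is 1/24 = 4.2% (passes), two are 2/24 = 8.3% (fails).
- Limit read per data point (section 14): Appendix A has 33 preoperative and operative rows, of which 27 apply whether or not a drain is placed. Counting only those, one blank among six patients is 1/(6 x 27) = 0.6%, well below 5%.

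The penalty is therefore real on one of the protocol's two wordings and negligible on the other. Neither says whether a field that does not apply counts as missing.

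**3. Size of the effect on the outcome**

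The protocol gives no figure for drain duration or for patients leaving hospital with a drain, so there is nothing to reproduce. The following are assumptions: removal time lognormal with median 4 days and log-SD 0.6, rounded up to whole days; a share q of drained patients lost, all with durations over 7 days but otherwise a random draw from those durations.

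Under this model:
- P(removal by POD 7) = Phi(ln(7/4)/0.6) = Phi(0.933) = 82.5%
- mean duration, all drains = 5.29 days
- mean duration, drains over 7 days = 10.62 days

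After losing a share q:
- observed mean = (5.29 - 10.62q)/(1 - q)
- observed proportion removed by POD 7 = 82.5%/(1 - q)

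| q | Mean (days) | Shift in mean | Removed by POD 7 | Shift |
|---|---|---|---|---|
| 2% | 5.18 | -0.11 | 84.1% | +1.7 points |
| 5% | 5.01 | -0.28 | 86.8% | +4.3 points |

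A 2-5% loss takes out 2/17.5 = 11% to 5/17.5 = 28% of all drains lasting more than 7 days. The centre of the distribution barely moves; the upper end is thinned noticeably.

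**The case against.** The strongest reply is that the protocol does not demand a removal day from every drained patient. Section 10 records secondary outcomes if they occurred, so a drain never removed has no removal to enter. The REDCap form is not shown and may have branching or a not-removed option. Removals after discharge can be picked up to POD 30 from clinic letters and re-attendances. The daily output chart to POD 10 and the length of stay give some indication of how long a drain was in.

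Part of this stands. No text tells anyone to invent a day, and the number affected may be small. But Appendix A is presented as the full list of required fields, and it offers no such option. Follow-up is limited to routine contacts, so a removal elsewhere may go unseen. Daily charts and length of stay allow a guess at drain status; they do not record it.

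A reader might infer something stronger: that deaths with the drain in place and accidental losses enter as early removals, making early removal look dangerous. The documents do not support that. Accidental withdrawal has its own reason code, day of death has its own field, and nothing asks for the day of death as a removal day. The protocol also specifies no comparison of mortality by removal day. If someone made one, the artefact would come mostly from the analysis. In a simulation with assumed rates (the removal times above, 30-day mortality 3-8%, death times exponential with mean 10 days capped at POD 30, accidental loss 3-5%, no true association), entering days of death or loss as removal days still gives a mortality ratio of about 1.0 for removal by POD 3 against later, once the comparison is restricted to patients alive after POD 3. Cleanly coded removals without that restriction give about 1.4.

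How drains not seen to be removed are handled in the analysis is commonly left to the statistical analysis plan. Its absence here is not part of this point.

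**Conclusion.** The point holds as a data-capture gap. The removal-day field cannot record a drain still in place; in survivors the resulting blank cannot be told from missing data; and the completeness rules discourage leaving it. The likely direction is a loss of long durations, so usual drain duration looks shorter.

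The effect is modest. At an assumed 2-5% loss confined to durations over 7 days, the mean falls by about 0.1-0.3 day and removal by POD 7 rises by about 2-4 points. These figures rest on the assumed removal-time distribution and on the unstated share of patients who leave hospital with a drain. If that share is near zero, so is the effect. The primary outcome, adherence on drain placement, is untouched. The case for acting is that the missing status may not be recoverable later and costs almost nothing to collect.

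**What to change.** Add a drain-status item beside the removal day in Appendix A and REDCap, completed for each drain:

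- removed, with POD;
- in place at death;
- in place at discharge or transfer, removal day not known, with the last day known in place;
- in place at POD 30.

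State in section 14 and Appendix D, step 9, that each category is a complete entry, and use the same unit (patients or data points) for the 5% limit in both places. The existing reason codes and the day-of-death field can stay as they are.

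Cost: one coded item with one conditional day, and a sentence in each of the two completeness passages. No extra patients, visits or procedures.

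### Drain output on the day of removal is a listed secondary outcome but has no field for drains removed after POD 10, and the daily window is not tied to a postoperative day

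*Protocol*

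**What the plan says.** **The outcome.** Section 7 of the protocol lists as a secondary outcome "Time (measured in whole days) until drain removal and drain output (quantity and contents) on day of removal". Section 10 has all secondary outcomes recorded from Day 0 (the day of surgery) to Day 30. Section 3 includes a secondary aim on when drains can be safely removed.

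**The collection rule.** Section 8: "Drain output (volume and contents) should be assessed daily until removal or for the first ten days after surgery", with the range given as Day 0 to Day 10.

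**The fields.** Appendix A, which section 9 cites together with REDCap as the full list of required data, has "Volume drained (Daily POD 1-10") and "Contents of drain output (Daily POD 1-10"). It also has "Day of drain removal", entered as a POD with no upper limit and no volume or contents attached. The only output item tied to removal is a qualitative reason (whether output was satisfactory, and if so why). It holds no millilitres and does not use the four contents categories.

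**The window.** Section 7: "Daily output will be calculated adding up the volumes drained in the 24 hours prior to the morning ward round". Section 8: "recordings of drain output must correspond to the entire day (8am to 8am"), followed by "It is advised that you collect data one day in retrospect to capture all relevant data". Appendix A repeats the 8am-to-8am wording and the advice on retrospective collection. No section says whether the 8am-to-8am window for a given POD ends or begins on that morning.

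**The concern.** An outcome defined on the day of removal needs a value on that day, whenever it falls. Here daily recording stops at POD 10, and no other field picks up the value for a later removal. Followed as written, the plan produces no volume or contents for those drains.

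The loss depends on how long the drain stays in, and that duration is the other half of the same outcome. Any summary of output at removal would describe only drains out by POD 10, although the aim concerns the timing of removal in general.

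A statistical analysis plan cannot repair this, because data that were never collected cannot be analysed. The quality controls would not reveal it either. The completeness rule in section 14 counts missing data points among existing fields, and validation re-collects key fields from Appendix A. Neither tests for an absent field.

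The second issue is comparability. If the window is not tied to a POD, two centres can both follow the text and enter different quantities for the removal day.

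**Working it through.** The protocol gives no figure for this point, so there is none to reproduce. The check is a count of covered days and a comparison of window definitions.

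**1. Coverage of possible removal days**

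- Recording period for secondary outcomes (section 10): POD 0 to 30, which is 31 days.
- Output assessed under section 8: POD 0 to 10, which is 11 days. Uncovered: 31 − 11 = 20 days (POD 11 to 30).
- Output fields in Appendix A: POD 1 to 10, which is 10 days. Uncovered: 31 − 10 = 21 days (POD 0 and POD 11 to 30).

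The wording of section 8 (until removal *or* for ten days) could be read loosely as whichever is later. The POD 1 to 10 fields settle it as a cap. These are counts of days, not shares of drains; removals need not be spread evenly over the period.

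**2. Share of drains affected: illustration only**

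The protocol gives no distribution of drain duration. Assume duration is log-normal with median m and log-SD s. Then P(T > 10) = 1 − Φ(ln(10/m)/s):

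| m (days, assumed) | s (assumed) | P(T > 10) |
|---|---|---|
| 4 | 0.6 | 6.3% |
| 5 | 0.6 | 12.4% |
| 4 | 0.8 | 12.6% |
| 5 | 0.8 | 19.3% |

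A simple assumed share of 2% would leave 20 of every 1,000 drains without the outcome; the four corners above would leave 63 to 193. The width of this range shows that the share is unknown. The gap itself does not depend on it.

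**3. The window**

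- *Backward reading.* Under section 7, the POD k value is the 24 hours ending at that morning's round. With a round at 08:00, this is exactly 08:00 on POD k−1 to 08:00 on POD k, itself an 8am-to-8am window. For a round at time t the overlap is 24 − |t − 8| hours: 23 at 07:00, 24 at 08:00, 22 at 10:00 (assumed times). From POD 2 on, a drain removed after the round contributes a full 24 hours.
- *Forward reading.* If the section 8 window instead runs from 08:00 on POD k, the removal-day entry ends when the drain comes out. Removal between 09:00 and 18:00 (assumed) gives 1 to 10 of 24 hours, or 4% to 42% of a day. At 10:00 it is 2/24 = 8.3%.

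**4. The start day**

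Section 8 starts at Day 0. Under the backward reading a Day 0 entry would end on the morning of surgery, before any drain exists for an operation starting after 08:00. A Day 0 start therefore fits the forward reading. Appendix A starts at POD 1, which fits the backward reading. The text does not decide between them for the 8am-to-8am window.

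**The case against.** **The windows agree.** A reader might infer that sections 7 and 8 prescribe windows one day apart, so that the removal day always holds only a part-day volume. The documents do not support that. No section labels a day by the 24 hours after 8am, and the advice to collect one day in retrospect concerns when to gather data. Section 7 is the only place that says which 24 hours count, and it looks backward. With a round near 8am the two windows nearly coincide. Section 8's insistence on the entire day also argues against entering a few hours. This objection stands. What remains is that the 8am-to-8am window is not expressly assigned to a POD, the round has no stated time, and the start days differ.

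**Day 0 is already covered.** Under the backward window the POD 1 entry contains drainage from the day of surgery after 08:00. This is correct under that reading, and then only a drain removed on POD 0 lacks an entry.

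**The bias is downward.** This too might be inferred, but for missing late removals it would require late drains to have higher output at removal. The protocol does not say so. Low volume is itself a listed reason for removal, so late drains may also come out at low output. A downward effect follows only for part-day entries, where they occur.

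**Other data serve the aim.** The day of and reasons for removal, radiological confirmation, and the days of later collections and leaks are all collected without a POD 10 cap. This limits the damage to the aim but does not supply the listed outcome.

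**REDCap may hold more.** Section 9 also points to the database, which cannot be seen here. A further field there is possible, but the written list would still need to show it.

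**Conclusion.** The gap is real and follows from the protocol's text alone. One component of a listed secondary outcome has no field for removals on POD 11 to 30, or on POD 0 in Appendix A. The loss selectively drops the longest-kept drains. How many drains are affected, and in which direction the summary would shift, cannot be determined from the protocol; the percentages shown rest wholly on assumed durations.

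The window point is smaller and is one of ambiguity: the removal-day value may be a full 24 hours or a part day, depending on how a centre reads section 8 and Appendix A.

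The primary outcome is unaffected, and so are the time to removal and the reasons for removal. The point still merits correction before data collection, because values not recorded at the time may not be recoverable.

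**What to change.** - Add one field per drain to Appendix A and the case report form: volume and contents in the 24 hours ending 08:00 on the day of removal, completed whatever the POD, up to Day 30. Where the drain was in place for less than 24 hours before that time, or was removed on POD 0, record the volume since insertion and mark it as a part day.
- State in sections 7 and 8 and in Appendix A that POD d output is the 24 hours ending 08:00 on POD d. This keeps section 7's backward window and replaces the unspecified round time with a clock time.
- Start the daily series at POD 1 in all three places, with the POD 1 value running from the end of surgery to 08:00 and marked as a part day.
- Amend section 8 so that the ten-day limit applies to the daily series and not to the removal-day value.

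The cost is one field per drain and aligned wording. It changes data recording only, not drain management.
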